7.5 Adjustments for Multiple Comparisons

The trial is designed with two hypothesis tested primary endpoints and five hypothesis tested secondary endpoints. The overall type I error will be controlled by serial gatekeeping approach with two families:

- 1. Set of two primary endpoints
- 2. Set of five powered secondary endpoints

Hypothesis testing of the two primary endpoints will occur first, with non-inferiority of the clinical outcome composite endpoint evaluated at one-sided alpha 0.05 and superiority of the valve function composite endpoint evaluated at one-sided alpha 0.025. Trial success will be declared if both endpoints are met at the prespecified alpha.

SMART Trial Statistical Analysis Plan	Form
Revision 5.0 Page 15 of 27	Medtronic

Hypothesis testing of the powered secondary endpoints will only occur when both primary endpoints are met. The family wise type I error rate for the powered secondary endpoints will be controlled using a fixed-sequence testing procedure, in which each endpoint will be tested hierarchically in prespecified order at a one-sided alpha 0.025 until a non-significant result occurs. For a given hypothesis test in the sequence, if the one-sided p-value is ≤ 0.025 , the next endpoint in the sequence will be evaluated. If the one-sided p-value >0.025, hypothesis testing will stop, and subsequent endpoints will not be evaluated for statistical significance.

Secondary endpoints will be tested in the following order:

- 1. MGV (Powered Secondary Objective #3)
- 2. EOA (Powered Secondary Objective #4)
- 3. HSVD (Powered Secondary Objective #2)
- 4. BVD in the female population (Powered Secondary Objective #1)
- 5. Moderate or severe PPM at 30 days (Powered Secondary Objective #5)

7.6 Demographic and Other Baseline Characteristics

Baseline demographics and clinical variables will be summarized descriptively by treatment arm for the ITT, AT, and Implanted analysis sets. Data will be summarized by treatment arm with standard descriptive summary statistics, including counts and percentages for categorical variables, and mean, standard deviation, median, first and third quartiles, and minimums and maximums for continuous variables. Continuous variables will be compared between treatment groups using a two-sample t-test or the non-parametric Wilcoxon rank-sum test, as appropriate. Categorical variables will be compared between treatment groups using a Chi-square test or Fisher's exact test, as appropriate. Ordinal variables will be compared using the Cochran-Mantel-Haenszel test with row mean scores.

7.7 Treatment Characteristics

Implant procedure data will be summarized by treatment arm for the AT analysis set as described for Demographic and Other Baseline Characteristics in **Section 7.6**.

7.8 Interim Analyses

No formal interim analyses are planned for the purpose of early stopping or sample size re-estimation.

7.9 Evaluation of Objectives

7.9.1 Primary Objective #1: Clinical Outcome Composite Endpoint

The clinical outcome composite endpoint in this trial is the composite of all-cause mortality, disabling stroke, or heart failure rehospitalization at 12 months post-procedure.

The endpoint is designed to show the Medtronic SE TAV is non-inferior to Edwards BE TAV in the composite event rate of all-cause mortality, disabling stroke or heart failure rehospitalization at 12 months post-procedure with an absolute non-inferiority margin of 8.0%. Formally, the hypothesis is as follows:

 $H_o: \pi_{MDT} \ge \pi_{EW} + \delta$

Revision 5.0

$H_A: \pi_{MDT} < \pi_{EW} + \delta$

In the above expression π_{MDT} and π_{EW} denote the composite event rates of all-cause mortality, disabling stroke, or heart failure rehospitalization at 12 months post-procedure for Medtronic SE TAV and Edwards BE TAV, and δ denotes the non-inferiority margin of 8%.

Non-inferiority of the clinical outcome composite endpoint will be based on the estimated event rate at 365 days for each arm from a Kaplan-Meier survival analysis. Components of the endpoint will be adjudicated by the CEC. Timing of event will be determined from the earliest component event for each subject and only events occurring within 365 days (12 months) will be considered in the analysis. Censoring time will be derived according to Section 7.2. The difference in the point estimates at 365 days will be assumed to be asymptotically normal and a two-sided large sample confidence interval for the difference in event rates will be calculated as follows:

$$(1 - \hat{S}_{MDT}) - (1 - \hat{S}_{EW}) \pm z_{\alpha/2} \sqrt{\hat{V}(\hat{S}_{MDT}) + \hat{V}(\hat{S}_{EW})},$$

where \hat{S}_{MDT} and \hat{S}_{EW} are the survival point estimates at 365 days from the Kaplan-Meier analysis for the Medtronic SE TAV and Edwards BE TAV, respectively, and $\hat{V}(\hat{S}_{MDT})$ and $\hat{V}(\hat{S}_{EW})$ are the Greenwood variance estimates corresponding to each survival point estimate. The test statistic for the noninferiority hypothesis will be calculated as

$$z = \frac{\left(1 - \hat{S}_{MDT}\right) - \left(1 - \hat{S}_{EW}\right) - \delta}{\sqrt{\hat{V}(\hat{S}_{MDT}) + \hat{V}(\hat{S}_{EW})}},$$

where δ is 8%, the non-inferiority margin.

The endpoint will be presented with the Kaplan-Meier estimate of the composite event rate at 365 days (cumulative incidence) within treatment arms along with corresponding Greenwood Standard error, the estimated difference in event rates (SE TAV – BE TAV) at 365 days with associated one-sided 95% upper confidence bound (i.e. upper confidence limit of the two-sided 90% confidence interval), and the p-value from the test statistic for non-inferiority. If the one-sided 95% upper confidence bound is less than the non-inferiority margin of 8%, the endpoint will be considered met at the one-sided alpha 0.05 level. The primary analysis of the clinical outcome composite endpoint will be performed using the AT analysis set. Sensitivity analyses will be conducted using the ITT and Implanted analysis sets. An additional sensitivity analysis will be performed for all subjects with attempted implant with treatment group based on randomized treatment assignment. If this population is the same as the AT analysis set, this additional sensitivity analyses will not be performed.

Components of the composite endpoint will be analyzed descriptively as part of Non-powered Secondary Endpoint 4 (Section 7.9.4).

7.9.2 Primary Objective #2: Valve Function Composite Endpoint

The valve function composite endpoint of BVD at 12 months post-procedure includes any of the following:

- HSVD: hemodynamic mean gradient \geq 20mmHg
- NSVD: severe PPM, or \geq moderate total aortic regurgitation (AR) •

Medtronic

Page 16 of 27

Revision 5.0

- Thrombosis
- Endocarditis
- Aortic valve re-intervention

The endpoint is designed to show the Medtronic SE TAV is superior to Edwards BE TAV in BVD at 12 months post-procedure. Formally, the hypothesis is as follows:

 $H_o: \pi_{MDT} \geq \pi_{EW}$

 $H_A: \pi_{MDT} < \pi_{EW}$

In the above expression π_{MDT} and π_{EW} denote the BVD rates at 12 months post-procedure for Medtronic SE TAV and Edwards BE TAV, respectively.

Components of the BVD endpoint will be reported on the echo core lab CRF and the CEC CRF.

Severe patient-prosthesis mismatch (PPM) is defined as follows and will be derived from data reported on the core lab TTE CRF:

- For subjects with BMI < 30 kg/m²: EOAI \leq 0.65 cm²/m²
- For subjects with BMI \ge 30 kg/m²: EOAI \le 0.55 cm²/m²

where BMI is the body mass index in kg/m^2 and EOAI is the Effective Orifice Area Index in cm^2/m^2 .

If BMI and/or BSA are not available at the visit, last observation carried forward method will be used in which the latest available BMI and/or BSA between baseline and follow-up echo will be used to calculate EOAI.

The endpoint will be evaluated using the point estimates at 365 days from a Kaplan-Meier analysis. Components of the valve function composite will be reported on the core lab transthoracic echocardiogram (TTE) CRF and the CEC CRF as follows.

- HSVD and NSVD will be detected on the core lab TTE CRF. Time to event for each will be based on the earliest detected occurrence up to and including the 12-month visit or through 395 days, whichever is later. Events based on the 12-month TTE which occur >365 days will be set to 365 days for the purposes of analysis. This approach allows counting of all HSVD and NSVD events found at the 12-month follow-up, even if the follow-up occurred after 365 days.
- Thrombosis, endocarditis, and aortic valve reintervention will be adjudicated by the CEC and derived based on the first component event. Only events within 365 days will be considered for the primary endpoint analysis.

For subjects that experience more than one component of the composite, the earliest event time will be used for the analysis. For subjects that do not experience any component of the composite within the timeframes described above, the censoring time will be the time of the latest echo known to be free of HSVD and NSVD (requires all evaluable data for all three of: effective orifice area, mean gradient, and aortic regurgitation).

The endpoint will be presented with the Kaplan-Meier estimate of the composite event rate at 365 days (cumulative incidence) within treatment arms along with corresponding Greenwood Standard error, the estimated difference in event rates (SE TAV - BE TAV) at 365 days with corresponding upper limit from the two-sided 95% large sample confidence interval, and the one-sided p-value for the superiority

Revision 5.0

Page 18 of 27

hypothesis. The two-sided confidence interval and test statistic will be calculated as described for the clinical outcome composite endpoint as

$$(1 - \hat{S}_{MDT}) - (1 - \hat{S}_{EW}) \pm z_{\alpha/2} \sqrt{\hat{V}(\hat{S}_{MDT}) + \hat{V}(\hat{S}_{EW})},$$

where \hat{S}_{MDT} and \hat{S}_{EW} are the survival point estimates at 365 days from the Kaplan-Meier analysis for the Medtronic SE TAV and Edwards BE TAV, respectively, and $\hat{V}(\hat{S}_{MDT})$ and $\hat{V}(\hat{S}_{EW})$ are the Greenwood variance estimates corresponding to each survival point estimate. The test statistic will be calculated as

$$z = \frac{(1 - \hat{S}_{MDT}) - (1 - \hat{S}_{EW})}{\sqrt{\hat{V}(\hat{S}_{MDT}) + \hat{V}(\hat{S}_{EW})}}$$

If the one-sided p-value is less than or equal to 0.025, the endpoint will be considered met. The components of BVD will be summarized descriptively. The analysis will be performed using the Implanted analysis set.

The following additional supportive analysis for the primary endpoint will be performed using the implanted population:

- Repeat analysis using Kaplan-Meier approach described above, excluding "late" 12-month echos (after end of 12-month visit window: 395 days).
- A tipping point analysis using the Kaplan-Meier estimate at 365 days that will systematically consider each subject with missing outcome at Day 365 as an event or a non-event at 365-days in all combinations.
- Complete case analysis based on the difference in binomial proportions with p-value calculated using a large sample test. This will be run including subjects with events within the timeframes described above for the primary analysis or with evaluable core lab echo (requires evaluable data for all three of: effective orifice area, mean gradient, and aortic regurgitation) free of BVD at 12 months.
- Non-parametric time to first event analysis estimating the cumulative incidence of the valve function composite endpoint while accounting for the competing risk of mortality, with endpoints and event times defined the same way as the primary analysis.
- Non-parametric survival analysis accounting for interval censoring, with the right boundary defined as the earliest event occurrence and the left boundary defined as the last day free of the valve function composite. The event rate estimates corresponding to the interval containing 365 days for each group will be reported, along with the hazard ratio comparing the groups and the p-value for the generalized log-rank test
- Survival analysis accounting for both interval-censoring and competing risk of mortality using the method described by Delord and Génin⁽⁷⁾. As above, the event rate estimates for each group at 365 days will be reported along with a hazard ratio comparing the groups and corresponding significance test.

Revision 5.0

Form

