7.2 General Methodology

Descriptive statistics of continuous outcomes will be presented by treatment arm and include count, mean, median, standard deviation, first and third quartiles, minimum and maximum. For categorical outcomes, the number and percentage of subjects in each category will be presented by treatment arm.

For time-to-event outcomes using Kaplan-Meier methods, the time points of 30 days, 1 year, 2 years, 3 years, 4 years, and 5 years will correspond to 30, 365, 730, 1095, 1460, and 1825 days post-implant, respectively. For each applicable time point, the event or event-free rate, the number of subjects at risk, the number of subjects with an event, the Greenwood standard error of the estimate, and the log-log transformed 95% confidence interval using the Greenwood standard error will be reported. For subjects with an event, the date of event will be based on the first event occurrence. For subjects without an event, date of censoring will be based on the latest of all follow-up visits, assessments, and events (for non-death events). Methods which account for interval censoring may be considered for survival analysis of events based on echo assessment.

For analyses using echocardiographic data, only echo data corresponding to the implanted study valve will be used; data post-explant or after reintervention will be excluded from analysis.

SMART Trial Statistical Analysis Plan Form Revision 5.0 Page 14 of 27 Mectronic

Subject data listings and tabular and graphical presentations of results will be provided. Unless otherwise specified, a two-sided 0.05 level of significance will be used to declare treatment arms significantly different.

All statistical analyses will be performed using SAS version 9.4 or higher (SAS Institute, Cary, North Carolina, USA) or other widely accepted statistical or graphical software.

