The endpoint will be derived following the same principles as described for the valve function composite co-primary endpoint in **Section 7.9.2**, with same method used for the primary analysis at 12 months. Cutoff days for point estimates are 730, 1095, 1465, and 1825 for analysis time points of 2 years, 3 years, 4 years, and 5 years, respectively. Time to event for events detected on scheduled follow-up echos at 2 years, 3 years, 4 years, and 5 years will be the minimum of the echo date or the visit target date (e.g., 365 days). As in the primary endpoint analysis, HSVD and NSVD events detected through the maximum of the annual visit echo date or the end of the corresponding visit window will be counted to ensure inclusion of events detected on unscheduled echos. Thrombosis, endocarditis, and aortic valve re-intervention events detected through the visit target date (730, 1095, 1465, and 1825 days respectively) will be counted. Components of the endpoint will also be reported at each time point. Analysis will use the Implanted analysis set.

Given the increasing impact of mortality on availability of the BVD endpoint at later time points, a survival analysis for interval-censored outcome data in the presence of competing risks will be performed as a supportive analysis, as described in the list of supportive analyses at the end of **Section 7.9.2**.

11. Echocardiographic measurements (i.e., EOA, mean gradient, PVL, LV mass regression, and DVI (severe <0.25, moderate 0.25-0.5, mild >0.5)) at discharge, 30 days, 12 months and annually to 5 years

Echocardiographic measurements will be summarized descriptively based on core lab reported data at each time point within arm. Analysis will be performed using the Implanted analysis set.

EOA and mean gradient will be analyzed as continuous data. Change from baseline in EOA and mean gradient will be summarized descriptively within each arm. Paravalvular leak (PVL) and DVI (severe <0.25, moderate 0.25-0.5, mild >0.5) will be analyzed descriptively as categorical data.

12. Mean gradient ≥ 20 mmHg based on stress echocardiogram at 12 months at select sites

Mean gradient \ge 20 mmHg based on stress echocardiogram at 12 months will be summarized descriptively as categorical data for each treatment arm. Stress echocardiogram will only be

SMART Trial Statistical Analysis Plan	Form
Revision 5.0 Page 25 of 27	Medtronic

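### Dysfunction first seen on an unscheduled echo after day 365 is inside the counting window but outside the date reset, so the day-365 estimate gives it no weight

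*SAP*

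**What the plan says.** SAP 7.9.2 fixes the readout for the valve function composite: "The endpoint will be evaluated using the point estimates at 365 days from a Kaplan-Meier analysis". Three further rules bear on HSVD and NSVD.

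- **Counting.** Time to event is "based on the earliest detected occurrence up to and including the 12-month visit or through 395 days, whichever is later". The source is the core-lab TTE form, and nothing limits it to the scheduled echo.
- **Reset.** "Events based on the 12-month TTE which occur >365 days will be set to 365 days for the purposes of analysis". The reason given is: "This approach allows counting of all HSVD and NSVD events found at the 12-month follow-up, even if the follow-up occurred after 365 days".
- **Default date.** SAP 7.2 says: "For subjects with an event, the date of event will be based on the first event occurrence". No other sentence re-dates an echo event at 12 months.

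For BVD at 2 to 5 years (SAP 7.9.4, endpoint 10), the SAP says that, as in the primary analysis, HSVD and NSVD events up to the later of the annual echo or the end of the visit window "will be counted to ensure inclusion of events detected on unscheduled echos". The SAP revision history for version 4.0 gives the same reason for the 12-month rule. Yet endpoint 10 caps the event date at the visit target only for scheduled echoes. Protocol 10.1.6 has assessments from unscheduled visits entered in the eCRFs.

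**The concern.** The counting rule and the reset rule differ in scope. The first reaches unscheduled echoes after day 365; the second does not. Because the estimate is read at day 365, an event that is counted but still dated day 366 or later carries no weight, and the subject enters the estimate as event-free at 12 months. The wider window then does nothing for the very echoes it was written to include.

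What is at stake is the accuracy and reproducibility of the reported rates for the second primary endpoint. The gap carries to BVD in females (SAP 7.9.3.1) and to HSVD so far as it is analyzed under 7.9.2 (SAP 7.9.3.2), both hypothesis-tested, and to the descriptive BVD endpoint at 2 to 5 years. Protocol 10.1.1 leaves subjects and site teams unblinded, so unscheduled imaging need not be balanced between arms.

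**Working it through.** **The plan's own figure.** SAP section 6 gives 60 per arm for 14% versus 36%, one-sided alpha 0.025, 80% power, pooled z-test. With a mean rate of 0.25:

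n = [1.960 × √(2 × 0.25 × 0.75) + 0.842 × √(0.14 × 0.86 + 0.36 × 0.64)]² / 0.22² = 59.6, so 60 per arm.

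The figure reproduces. The point concerns a derivation rule, so the rule itself has to be traced.

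**Tracing the rule as written**

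| Subject | Counted? | Date | Weight at day 365 |
|---|---|---|---|
| 12-month TTE positive on day 380, no other echo | yes | reset to 365 | yes |
| Unscheduled echo positive on day 380, 12-month TTE negative or not evaluable | yes | 380 (default) | none |
| Unscheduled echo positive on day 372, 12-month TTE positive on day 390 | yes | 365 if the reset comes first; 372 if the earliest detection is picked first | depends on the order |

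The second row is the clear case. If the 12-month TTE is done after day 395, the counting window, and with it the gap, runs on to that visit.

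**Do the supportive analyses in 7.9.2 close the gap?** The tipping-point analysis varies only subjects whose day-365 outcome is missing, and these are not missing. The competing-risk analysis takes event times defined as in the primary analysis, so it inherits the gap. The complete-case proportion counts events inside the primary timeframes, so it scores the second-row subject as an event. The interval-censored analyses do not rely on the reset.

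**Size.** Assume 350 per arm (700 as-treated subjects, 1:1), the planning rates (0.14 × 350 = 49 SE events and 0.36 × 350 = 126 BE events) and no censoring before day 365. Then 1 − S(365) = d/350, the Greenwood variance reduces to p(1 − p)/350, and each unweighted event lowers its arm's rate by 1/350 = 0.29 points. With earlier censoring each such event would weigh at least this much. The documents do not give k, the number of affected subjects, so a range is shown.

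| k in SE | k in BE | SE rate | BE rate | Difference (points) | z |
|---|---|---|---|---|---|
| 0 | 0 | 14.00% | 36.00% | −22.00 | −6.95 |
| 1 | 1 | 13.71% | 35.71% | −22.00 | −6.98 |
| 5 | 5 | 12.57% | 34.57% | −22.00 | −7.10 |
| 10 | 10 | 11.14% | 33.14% | −22.00 | −7.27 |
| 0 | 5 | 14.00% | 34.57% | −20.57 | −6.54 |
| 0 | 10 | 14.00% | 33.14% | −19.14 | −6.12 |
| 5 | 0 | 12.57% | 36.00% | −23.43 | −7.51 |
| 10 | 0 | 11.14% | 36.00% | −24.86 | −8.10 |

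With every counted event after day 365 reset, the first row holds for any k. The test needs z ≤ −1.96.

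**Later years.** By the visit windows in Protocol 10.3, the exposed stretch past target is 760 − 730 = 30 days at year 2 and 60 days at years 3 to 5 (for example 1155 − 1095).

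**The case against.** The strongest reply is that the SAP never says an unscheduled-echo event keeps its own date. It says such events are to be counted, and an event counted toward a day-365 estimate has to be dated by day 365. On that view the text is silent on a detail and a sensible programmer would fill it in. The first part is fair: the late date follows from the default in 7.2 and the limited scope of the reset, not from an explicit instruction. But the reset sentence names the echoes it applies to, so filling the gap means overriding stated scope. SAP section 8 plans independent validation of the hypothesis-tested endpoints, and two programmers could reasonably differ here.

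A second reply is that few subjects can be affected. This stands. Days 365 to 395 are the 12-month visit window itself, so most echoes then will be the 12-month TTE, and where the scheduled echo is missing an in-window echo may be classed as the 12-month TTE. HSVD is also arguable, because 7.9.3.2 refers to core-lab data at 12 months.

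A third reply is that setting such events to day 365 is not free. With a negative 12-month TTE on day 366 and a positive unscheduled echo on day 390, the event would be dated before an echo that showed none. This also stands. SAP 7.9.2 cuts the adjudicated components at day 365, so whether to count such an event is a real choice; for echo events the SAP has already chosen to count it.

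A reader might go further and infer that an extra positive echo causes a positive 12-month TTE to be lost. The documents do not support that. SAP 7.9.2 uses the earliest event time when a subject has more than one component event; if the scheduled finding is reset first, day 365 precedes day 372 and the event counts. That order fits the stated purpose better. The SAP leaves the order open, and no more than that can be claimed.

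**Conclusion.** The point holds as a reset rule narrower than the counting rule it serves. As written, a positive unscheduled echo after day 365 but within the counting window has no weight in the primary estimate when the 12-month TTE is negative or not evaluable. That runs against the SAP's stated intent and against its own complete-case analysis. When both echoes are positive, the outcome is undefined until the order of steps is stated.

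The size is about 0.29 points per affected subject, assuming 350 per arm and no censoring before day 365. The number of such subjects is unknown and likely small. A reader might infer that the superiority finding is at risk; the figures do not support this. With up to 10 such events in either or both arms, z stays between about −6.1 and −8.1 at the planning rates. Endpoint 10 is descriptive, so no test depends on it. The correction is worth making because it bears on how a primary rate is derived and costs little.

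**What to change.** In SAP 7.9.2, replace the reset sentence with wording such as: *Any HSVD or NSVD event counted for the 12-month analysis, from a scheduled or unscheduled echo, that is dated after day 365 is set to day 365. This is done before the earliest event time is selected.* BVD in females, and HSVD as analyzed under 7.9.2, then follow.

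In SAP 7.9.4, endpoint 10, date every counted echo event at the smaller of the echo date and the visit target date, whether or not the echo was scheduled. Settle the year-4 target at the same time: SAP 7.2 uses day 1460 and endpoint 10 uses day 1465.

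The cost is one sentence in each section and a line of derivation code, with no change to data collection. The small downside is that an event may be dated before a negative 12-month TTE done between day 365 and the unscheduled echo. List those subjects by arm so that readers can see how many there are.

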- Primary Objective #2 Valve Function Composite Endpoint: The valve function composite endpoint is designed to evaluate the superiority of the Medtronic SE TAV to Edwards BE TAV in BVD at 12 months post-procedure. Under the assumptions of 14.0% event rate for Medtronic SE TAV, 36% event rate for Edwards BE TAV, superiority hypothesis, one-sided alpha 0.025, and 1:1 randomization ratio, based on the pooled z-test a minimum evaluable sample size of 120 subjects (60 per arm) would provide 80% power for the endpoint. Assumptions for the valve function composite endpoint were based on historical data from prior randomized trials evaluating the Medtronic SE TAV compared to SAVR in the low, intermediate, and high surgical risk populations¹.
- Powered Secondary Endpoint #1 BVD in Female Population: Powered secondary endpoint #1 aims to evaluate superiority of the Medtronic SE TAV to Edwards BE TAV in BVD at 12 months post-procedure in the female population. Assumptions for the endpoint are the same as the valve function composite endpoint and therefore the minimum required sample size is 120 subjects (60 per arm). With a total sample size of 700 as-treated subjects of which approximately 80% are expected to be female, the trial sample size will be adequate to power the endpoint within the female population.
- Powered Secondary Endpoint #2 HSVD: Powered secondary endpoint #2 is designed to evaluate the superiority of the Medtronic SE TAV to Edwards BE TAV in HSVD at 12 months post-procedure. Under the assumptions of 4.0% event rate for the Medtronic SE TAV, 19.0% event rate for the Edwards BE TAV, superiority hypothesis, one-sided alpha 0.025, and 1:1 randomization ratio, based on the pooled z-test a minimum evaluable sample size of 140 subjects (70 per arm) would provide 80% power for the endpoint. Assumptions for the anticipated rate of HSVD were based on historical data from prior randomized trials evaluating the Medtronic SE TAV compared to SAVR in the low, intermediate, and high surgical risk populations¹.

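### The 12-month BVD analysis sets a time limit for events but none for the censoring echo, so the reported BVD rates can read too low where 12-month echoes are missing

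*SAP*

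**What the plan says.** SAP 7.9.2 defines the analysis of the second primary endpoint: "The endpoint will be evaluated using the point estimates at 365 days from a Kaplan-Meier analysis". Its time limits differ by component.

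- **HSVD and NSVD (core-lab echo):** the event is the "earliest detected occurrence up to and including the 12-month visit or through 395 days, whichever is later". Late positives are pulled back: "Events based on the 12-month TTE which occur >365 days will be set to 365 days for the purposes of analysis".
- **Thrombosis, endocarditis and re-intervention (CEC):** "Only events within 365 days will be considered for the primary endpoint analysis".
- **No event within those limits:** "the censoring time will be the time of the latest echo known to be free of HSVD and NSVD". To count as clean, that echo "requires all evaluable data for all three of: effective orifice area, mean gradient, and aortic regurgitation".

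The censoring echo has no latest date, and neither document states a data cut for the 12-month analysis. Protocol 10.1.5 schedules echoes every year to year 5.

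The same method serves two powered secondary endpoints, BVD in women (SAP 7.9.3.1) and HSVD (7.9.3.2). For BVD at 2 to 5 years, SAP 7.9.4 #10 states: "The endpoint will be derived following the same principles as described for the valve function composite co-primary endpoint".

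**The concern.** Take two subjects with a clean 30-day echo and no evaluable 12-month echo. The first has a clean 2-year echo, is censored near day 730, and counts as event-free at day 365. The second has a positive 2-year echo. That finding lies outside the event limit, so the subject is censored at the 30-day echo and has left before day 365.

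Membership of the day-365 risk set thus depends on a later outcome, and the rule adds only event-free subjects to the denominator. The affected group is not only those who miss the visit. Protocol 10.1 allows follow-up by telephone, and an echo that lacks any one of the three required measurements also fails to count as clean.

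At stake are the absolute BVD rates in each arm for a primary endpoint, two powered secondary endpoints, and the long-term valve function results that form the trial's secondary objective.

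**Working it through.** **1. The plan's own figure.** SAP section 6 assumes: "Under the assumptions of 14.0% event rate for Medtronic SE TAV, 36% event rate for Edwards BE TAV". With one-sided alpha 0.025, 80% power and a pooled z-test:

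n = [1.960·√(2·0.25·0.75) + 0.842·√(0.14·0.86 + 0.36·0.64)]² / 0.22² = 59.6, so 60 per arm.

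This matches the SAP. The censoring rule does not change it.

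**2. Share with a later echo.** The documents give 20 months (about 609 days) of enrolment. Assume uniform accrual and a data cut when the last subject reaches day 395. The share past day 730 is (609 + 395 − 730)/609 = 45%. It is 50% past day 700 and 40% past day 760, the ends of the 2-year window. A later cut raises these shares.

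**3. Closed form.** Let m be the share without an evaluable 12-month echo (not in the documents; 5-20% assumed, independent of BVD status). Let f be the share of those with a later echo, h the true 12-month rate among those still free of BVD, and r the new BVD between month 12 and the later echo. The day-365 step is

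(1−m)h / [(1−m) + m·f·(1−h)(1−r)].

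With the censoring echo capped at the event limit, the second term of the denominator drops out and h is returned.

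For BE with m = 10%, f = 45%, r = 0 and no BVD found by day 30: 0.324/(0.9 + 0.045·0.64) = 34.9%. For SE: 0.126/(0.9 + 0.045·0.86) = 13.4%.

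| m | f | SE (true 14.0) | BE (true 36.0) | Bias SE / BE (points) | Difference (true 22.0) |
|---|---|---|---|---|---|
| 5% | 45% | 13.7 | 35.5 | −0.3 / −0.5 | 21.7 |
| 10% | 45% | 13.4 | 34.9 | −0.6 / −1.1 | 21.5 |
| 20% | 45% | 12.8 | 33.6 | −1.2 / −2.4 | 20.8 |
| 20% | 100% | 11.5 | 31.0 | −2.5 / −5.0 | 19.5 |

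The last row is an analysis run after every 2-year echo is in. Setting r = 5% changes the 45% rows by about 0.1 point or less. At 350 per arm, power exceeds 99% in every row.

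**4. Early detection.** If half of BVD is found by day 30, the bias at m = 10%, f = 45% is −0.3 (SE) and −0.7 (BE).

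**5. Simulation check (200,000 per arm, echo dates spread over the visit windows).** With no early BVD, the SAP's rule gives 13.44% and 34.97% at m = 10%, and 12.76% and 33.55% at m = 20%. The capped rule gives 14.04% and 36.15%, then 13.94% and 35.95%. These agree with the formula.

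With half of BVD found early, the SAP's rule gives 13.98% and 35.75% (m = 10%) and 13.83% and 35.47% (m = 20%). The capped rule gives 14.32% and 36.63%, then 14.55% and 37.19%. The gap between the rules (0.3 and 0.9, then 0.7 and 1.7 points) is of the size the formula predicts, but the capped rule itself sits above the truth. The cause is separate: subjects with no 12-month echo leave on the date of their own 30-day echo, while 30-day positives in others are recorded up to day 45. The two errors partly cancel, so the net shortfall against the truth is smaller here.

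**6. Unequal missingness, no true effect.** With 25% BVD in both arms, m = 20% in SE and 10% in BE, and f = 45%: SE 0.200/0.8675 = 23.1%, BE 0.225/0.93375 = 24.1%. That is a false difference of −1.0 point. At f = 100% it is −2.0.

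**7. Is a cap enough?** Suppose no 12-month echo is missing, but 10% are done at day 350 (assumed). In BE with no early BVD, the day-350 step leaves 0.964 free.

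- **Cap only:** the 6.4% with a clean echo leave before the events at day 365. Free: 0.964·(1 − 32.4/90) = 0.617, a rate of 38.3%.
- **SAP's rule, 45% with a later clean echo:** 0.964·(1 − 32.4/92.88) = 0.628, a rate of 37.2%.
- **Cap, with clean early visit echoes moved to day 365:** 0.964·(1 − 32.4/96.4) = 0.640, a rate of 36.0%, the true value.

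**The case against.** A reader might infer that the plan ignores every later positive echo. It does not. Positives count up to the later of the 12-month visit and day 395, including a late 12-month echo and unscheduled echoes in that period. Only findings beyond that limit are lost.

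The size depends on inputs the documents do not give: the share without an evaluable 12-month echo, the data cut, and the share of BVD found early. That stands, which is why ranges are shown. If the dataset ends at the 12-month limit, the problem disappears.

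A reader might also infer that the superiority claim is in danger. With equal missingness the bias shrinks the difference, which works against the sponsor. A false gain for SE needs more missing 12-month echoes in SE than in BE. The trial is open to subjects and sites, so this is possible, but nothing in the documents suggests it.

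The planned supportive analyses help in part. The complete-case analysis requires an event or a clean evaluable 12-month echo, and so avoids the flaw. The interval-censored analysis could use later positives if they are kept as events. The tipping-point analysis varies only subjects with a missing day-365 outcome, so it would pass over those classed as event-free by a later clean echo. The competing-risk analysis keeps the same event definitions and times. None of them corrects the primary estimate.

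Finally, a cap alone can make the estimate worse when clean 12-month echoes are done before day 365 (step 7). This is correct. Protocol 10.3 keeps out-of-window visits in the analysis, and the windows for years 2 to 5 open 30 to 60 days before the target day. The fix has to deal with it.

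**Conclusion.** The point holds as a flaw in the estimated rates. Two conditions must be met: some subjects lack an evaluable 12-month echo, and the dataset contains echoes after the event limit. With 12-month echoes missing at random, 5-20% missing, 45% with a later echo and no BVD found by day 30, the BVD rate is understated by about 0.5-2.4 points in BE and 0.3-1.2 in SE. In closed form this is roughly halved if half of BVD is found by day 30, and the spread of 30-day echo dates can offset part of the rest.

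The documents do not support the stronger readings that the estimate is always too low or that the test is compromised. Early visit echoes push the rate the other way, and power stays above 99% with equal missingness. The effect could favour SE only if more SE than BE subjects lack a 12-month echo.

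The same rule reaches BVD in women, HSVD and the later BVD estimates. After the 5-year visit no further echo is scheduled, so the exposure there is mainly at years 2 to 4.

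**What to change.** In SAP 7.9.2, replace the censoring sentence with wording such as:

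> For the 12-month estimate, echoes after the later of the 12-month visit and day 395 are not used, whether positive or negative. Subjects without an event are censored at the latest fully evaluable clean echo within that limit. If that echo is the 12-month visit echo and was done before day 365, the censoring time is set to day 365.

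Apply the same cap, and the same move to the target day, at each annual visit in 7.9.4 #10. The 4-year target day should be settled at the same time, because SAP 7.2 gives 1460 and 7.9.4 #10 gives 1465.

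The cost is a few sentences of SAP text, with no change to sample size or data collection. A few subjects without an evaluable 12-month echo leave the day-365 risk set, and a clean early visit echo is taken as event-free to the target day. The change does not remove the separate effect of spread 30-day echo dates (step 5), which the cap leaves without its partial offset. Dating all 30-day visit echoes to one common day would deal with that, if the sponsor wishes.
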